5.1. General Statistical Considerations

All statistical analyses will be performed using SAS® version 9.0 or higher. The specific analyses to address the objectives will be described in the Statistical Analysis Plan.

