Like the analysis for primary objective 2, kappa statistics will be used to assess inter-reader reliability of flortaucipir F 18 PET scan visual interpretation with a τAD++ pattern. Fleiss' Kappa and the associated 95% CI will be calculated based on 5 readers' visual interpretations on the 242 scans (comprised of 83 scans from Study A16 autopsy cases, and 159 cases from Study A05). The p-value will be calculated using a normal approximation method. The lower bound of the 95% CI for Fleiss' Kappa must be greater than or equal to 0.6 to meet the inter-reader reliability criterion. If the scan is selected (by random) to be read twice for the intra-reader reliability assessment, the first read will be used for this analysis; for Study A16 SAC cases, the overall reads (using both hemispheres) from each reader will be used for this analysis.

5.4.2.3. Analysis for Secondary Objective 3

For this objective, inter-reader reliability of flortaucipir F 18 PET scan visual interpretation in the Study A05 scans, a population similar to the intended population for clinical use will be assessed similar to the second primary objective analysis except that the Fleiss' Kappa will be calculated based on 5 readers' visual interpretations on the 159 scans from Study A05. If any of the scans are selected (by random) to be read twice for the intra-reader reliability assessment, the first read will be used for this analysis. As an exploratory analysis, a similar analysis will be conducted using Study A16 scans.

5.4.2.4. Analysis for Secondary Objective 4

Twenty scans will be randomly selected for this analysis, and the 5 readers will read them in random sequence along with other scans. Cohen's Kappa will be calculated for each of these 5 readers, based on these 20 scans read repeatedly to assess the intra-reader reliability of flortaucipir F 18 PET scan visual interpretation. The 95% CI as well as p-values will be calculated using normal approximation method.

6. Study Documentation

Avid will be responsible for the submission of the protocol to the Instututional Review Board/Independent Ethics Committee for regulatory approval prior to start of the study.

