6. FLORTAUCIPIR PET SCAN SELECTION

Flortaucipir F 18 PET scans were selected from subjects enrolled in previous studies ^{18}F -AV-1451-A16 and ^{18}F -AV-1451-A05. The following images will be used for this study:

- All 83 subjects from Study A16 (primary and supplemental) who have a valid scan and autopsy. This includes:
 - 3 front-runners
 - 64 main study autopsy cases
 - 16 autopsy cases collected under SAC
- All 159 subjects from the study ^{18}F -AV-1451-A05 who have a valid scan, representing the intended population for clinical use.
- 20 scans will be randomly selected (by simple random selection method) from studies A16 and A05, to be read twice independently by each of the 5 readers for intra-reader reading reliability evaluation purposes.

The majority read results from A05 and A16 both showed a ~56% scan positive ($\tau\text{AD}^+/\tau\text{AD}^{++}$) rate. Similarly, it is expected that the 20 scans randomly selected for intra-reader reliability evaluation will have a similar scan positive rate. If by chance the randomly selected 20 cases have a skewed positive or negative rate, to avoid possible interpretation bias from a sample population of primarily positive or negative scans, the random sampling process will be repeated to ensure a relatively balanced positive/negative rate from the selected samples (scan positive rate by majority reads from corresponding study is in the range of 30% - 70%).

An external CRO will randomize all scans into a randomized sequence for visual reading.

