The subjects enrolled in study A05 were representative cases of the intended clinical use population for flortaucipir F 18 scan. This analysis will evaluate the inter-reader reliability of flortaucipir scan interpreted as AD pattern with this intended clinical practice population. Analyses similar to 10.3.3 will be conducted using EFP2, which will be based on 159 A05 cases as defined in 7.2.2.2.

10.4.4. Intra-Reader Agreement of Flortaucipir F 18 PET Scan Visual Interpretation Interpreted as AD Pattern

Intra-reader reliability will be assessed using randomly selected 20 cases (EFP3) as defined in section 7.2.2.3. These randomly selected cases will be read twice by every reader. A Cohen's Kappa statistics will be used to assess the agreement of the two reading results (scans that are interpreted as an AD pattern, i.e., τ AD (τ AD+/ τ AD++) vs τ AD-) by every reader.

The percent of agreement between the two readings from same reader will be calculated for each reader. All these results will be summarized in tables.

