10.5. Other Efficacy Analyses

10.5.1. Accuracy of Flortaucipir F 18 Scan in Detecting Tau Neurofibrillary Pathology Associated with Alzheimer's Disease (AD), Based on Majority Scan Interpretations

For each image, the majority interpretation of 5 independent readers will be derived using individual readers' interpretation results. Diagnostic performance of this majority interpretation will be assessed relative to the autopsy NFT score TS as per primary objective #1 efficacy analysis #1 (refer to Section **Error! Reference source not found.**0.3.1) and again relative to the NIA-AA autopsy diagnosis TS as per primary objective #1 efficacy analysis #2 (refer to Section **Error! Reference source not found.**0.3.2).

The sensitivity and specificity along with their two-sided 95% CIs (based on the Wilson score method) will be calculated for the majority interpretation of 5 independent readers relative to the appropriate TS.

The accuracy, PPV, NPV, LR+ and LR- of the flortaucipir F 18 PET imaging classification for the majority interpretation of 5 independent readers relative to the appropriate TS will be also calculated. Two-sided 95% CIs (based on the Wilson score method) will be provided for the accuracy, the PPV and NPV.

10.5.2. Inter-Reader Agreement of Flortaucipir F 18 PET Scan Interpreted as AD Pattern for Autopsy Population

The inter-reader agreement analysis across 5 readers of flortaucipir F 18 PET scan interpretation (interpreted as AD pattern) will be repeated based on the EFFA. Fleiss' Kappa, and other statistics, will be calculated the same as described in section 10.3.3.

10.5.3. Additional Visual Interpretation Reliability Assessment of Flortaucipir F 18 Scan Interpreted as τ AD++ Pattern

These additional visual interpretation reliability assessments will be conducted for flortaucipir F 18 scans based on the τ AD++ pattern:

1) Inter-reader reliability for scans including clinical use population only (A05 cases):

Fleiss' Kappa, and other statistics will be calculated the same as described in section 10.3.3., based on EFFP2.

2) Inter-reader reliability for scans including autopsy cases only (A16 cases):

Fleiss' Kappa, and other statistics will be calculated the same as described in section 10.3.3., based on EFFA.

3) Intra-reader reliability for scans included in EFP3:

Cohen’s kappa and other statistics will be calculated the same as described in section 10.4.4, based on EFP3.

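### Intra-reader kappa on 20 scans: the normal-approximation 95% CI collapses to [1, 1] at perfect agreement and covers below 95% elsewhere

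*Protocol*

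**What the plan says.** Protocol 5.4.2.4 sets the sample: "Twenty scans will be randomly selected for this analysis, and the 5 readers will read them in random sequence along with other scans". It calculates one Cohen's kappa for each of the five readers, "based on these 20 scans read repeatedly to assess the intra-reader reliability", and then says: "The 95% CI as well as p-values will be calculated using normal approximation method".

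Protocol 5.1 passes the detail on: "The specific analyses to address the objectives will be described in the Statistical Analysis Plan". SAP 10.4.4 confirms the design ("These randomly selected cases will be read twice by every reader") and defines the comparison as AD pattern against no AD pattern, so each reader contributes one 2x2 table of 20 scans. It adds percent agreement ("The percent of agreement between the two readings from same reader will be calculated for each reader") but mentions no confidence interval for either statistic. SAP 10.5.3(3) repeats the analysis for the τAD++ pattern by cross-reference: "kappa and other statistics will be calculated the same as described in section 10.4.4, based on EFP3". Neither document has a rule for perfect agreement.

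SAP section 6 reports a positive rate of about 56% by majority read in both source studies. It repeats the draw of the 20 scans unless the "scan positive rate by majority reads from corresponding study is in the range of 30% - 70" percent.

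**The concern.** Normal approximation for a kappa CI is naturally read as estimate plus or minus 1.96 standard errors (a Wald interval). That method suits large samples with kappa well inside its range. Here there are 20 pairs, and a reader repeating his or her own reads may well show high agreement, which is where the method fails.

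This is the only uncertainty statement specified for a named secondary objective. A reader with no discordant pair would be reported with an interval of zero width. Other readers could get upper limits above 1, which kappa cannot reach. If the lower limit is too high too often, the report overstates how well intra-reader reliability has been established.

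**Working it through.** **Inputs.** n = 20 scans per reader, normal-approximation 95% CI (Protocol 5.4.2.4); two-sided 0.05 level (SAP 10.1); positive rate π = 0.56, with 0.30 and 0.70 as bounds (SAP section 6). The true intra-reader kappa is not given, so κ = 0.6 to 0.95 is assumed. The documents state no precision or coverage figure for this analysis, so there is none to reproduce.

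**Formulas.** κ̂ = (po − pe)/(1 − pe), where po is observed and pe is chance agreement. The standard large-sample variance is SE² = (A + B − C)/[n(1 − pe)²], with
- A = Σ p_ii[1 − (p_i. + p_.i)(1 − κ̂)]²
- B = (1 − κ̂)² Σ_{i≠j} p_ij(p_.i + p_j.)²
- C = [κ̂ − pe(1 − κ̂)]²

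**Step 1: perfect agreement.** With no discordant pair κ̂ = 1, so A = Σ p_ii = 1, B = 0 and C = 1. Hence SE = 0 and the CI is [1, 1], whatever the split of positives and negatives.

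**Step 2: one or two discordant pairs.** For 11 both positive, 1 discordant, 8 both negative: po = 0.95; pe = 0.60 × 0.55 + 0.40 × 0.45 = 0.51; κ̂ = 0.44/0.49 = 0.898; SE = 0.0989; CI = 0.898 ± 1.96 × 0.0989 = 0.704 to 1.092. For 10 both positive, 1 + 1 discordant, 8 both negative: κ̂ = 0.798 and CI = 0.532 to 1.064.

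**Step 3: exact coverage.** All 2x2 tables with n = 20 were enumerated under a multinomial model with the same positive rate at both reads. Each discordant cell then has probability π(1 − π)(1 − κ), and P(20/20) = [1 − 2π(1 − π)(1 − κ)]^20. For example, at π = 0.56 and κ = 0.8 this is (1 − 0.0986)^20 = 12.6%.

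| True κ | Wald coverage, 56% positive | Wald coverage, 30% or 70% positive | P(20/20), 56% positive | Goodness-of-fit coverage, 56% positive |
|---|---|---|---|---|
| 0.6 | 91.2% | 88.7% | 1.2% | 95.1% |
| 0.7 | 86.6% | 89.0% | 4.1% | 95.7% |
| 0.75 | 91.7% | 87.6% | 7.2% | 95.9% |
| 0.8 | 86.4% | 81.5% | 12.6% | 95.5% |
| 0.85 | 78.0% | 72.1% | 21.5% | 94.1% |
| 0.9 | 63.3% | 57.3% | 36.4% | 92.6% |
| 0.95 | 39.2% | 34.5% | 60.7% | 91.4% |

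**Step 4: direction of the misses.** At 56% positive the lower limit is too high in 11.9% of samples at κ = 0.7, 12.6% at 0.8 and 36.4% at 0.9. The upper limit is too low in at most 1.5% over κ = 0.7 to 0.95.

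**Step 5: how often the collapse would be seen.** If the five readers are treated as independent, the chance that at least one scores 20/20 is 1 − (1 − P)^5: about 19% at κ = 0.7, 49% at 0.8 and 90% at 0.9 (56% positive).

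**Step 6: what 20/20 supports.** The goodness-of-fit interval keeps every κ for which the chi-square distance between the observed counts (both positive, discordant, both negative) and those expected is at most 3.84. With 11 positive, 9 negative and no discordance, p = 0.55. Setting u = p(1 − p)(1 − κ), the distance is 20[2u + u²/(p − u) + u²/(1 − p − u)]. At κ = 0.675, u = 0.0804 and the distance is 3.84, so the interval is 0.675 to 1. The tables in step 2 give 0.519 to 0.982 and 0.393 to 0.944.

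**Step 7: p-value.** Neither document states the null value or which SE is used. For κ = 0, the exact two-sided type I error with the null SE is 5.1% (56% positive) and 4.5% (30%). With the non-null SE used for the CI it is 8.5% and 15.9%. At 20/20 the null SE gives z = √20 = 4.47, so that test stays defined.

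**The case against.** The strongest reply concerns weight. Secondary objective 4 has no acceptance threshold, and SAP 10.2 ties trial success to the three primary analyses only, so no decision depends on this interval. Percent agreement on a fixed 20 scans is tabulated per reader, so a reader of the report can see 20/20. All of that stands and limits the point to reporting.

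Second, from κ = 0.75 upward the lower-limit misses are exactly the 20/20 samples. Given at least one disagreement, coverage at 56% positive is 98.8% at κ = 0.75 and at 0.8. The lowest figures in the table therefore restate how often the collapse occurs and are not a second defect. This is correct. Separate under-coverage remains at lower values: given a disagreement, coverage is 92.3% at κ = 0.6 and 90.3% at 0.7.

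Third, the coverage figures rest on assumed kappas. The only stated kappa is 0.7, for inter-reader Fleiss' kappa. The 30%/70% column is a bounding case, because the SAP's redraw rule would reject many samples that an unrestricted draw at 30% produces. The 0.675 limit belongs to the 11/9 split; at 6/14 or 14/6 it is 0.63. These are fair limits, but the 56% column is below 95% at every kappa tried.

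Fourth, the goodness-of-fit interval is not exact either: 93.1% at κ = 0.65 and 91.4% at 0.95 (56% positive). That is true, and it is still far closer to nominal. Finally, the p-value point is a gap in specification and not a shown error.

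**Conclusion.** The concern holds. The one stated method gives a zero-width interval whenever a reader has no discordant pair; this is algebra and needs no assumption. At 56% positive its coverage is about 86% to 92% for a true kappa of 0.6 to 0.8, falling to 63.3% at 0.9 and 39.2% at 0.95, with errors mainly on the favourable side. The coverage figures assume equal positive rates at the two reads, the usual large-sample SE and the stated range of kappa. They apply to the AD-pattern comparison; the documents give no τAD++ rate for the parallel analysis in SAP 10.5.3(3), but the collapse applies there too. The change should be made, although no success criterion depends on it.

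**What to change.** - In Protocol 5.4.2.4, replace the normal-approximation CI with a small-sample interval for kappa, such as the goodness-of-fit (score-type) interval. Name the same method in SAP 10.4.4 and 10.5.3(3).
- Give each reader's percent agreement a Wilson interval, the method already used for accuracy. At 20/20 its lower limit is 20/(20 + 1.96²) = 83.9%.
- Keep the p-value, but state the null (kappa = 0) and that the null SE is used.

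A smaller change is to keep the Wald interval and pre-specify the goodness-of-fit limit for zero disagreements only. That gives 98% to 99.9% coverage from κ = 0.75 upward, but still only 90.7% at κ = 0.7 (56% positive).

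The cost is one sentence in the protocol, two in the SAP and a small program. Lower limits become less favourable, and coverage still falls to about 91% to 93% at κ = 0.95.

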6.1. Investigators (Readers)

Readers must supply Avid with the following documentation prior to performing any tasks associated with this protocol:

- Signed and dated 1572
- Signed and dated curriculum vitae
- Medical license
- Financial disclosure form

In order to ensure blinding, readers will not be provided a copy of the protocol for review; therefore, a Protocol Signature Page will not be collected as part of the trial master file.

1. LIST OF ABBREVIATIONS

Table 1: List of Abbreviations

AD	Alzheimer's Disease
CN	Cognitively Normal
TS	Truth Standard
MCI	Mild Cognitive Impairment
SAP	Statistical Analysis Plan
CRO	Contract Research Organization
ODD	Other Dementia Disorder
τAD-	Not consistent with AD pattern
τAD	AD pattern
CRF/eCRF	Case Report Form/ Electronic Case Report Form
SAS	SAS® software
ADNC	AD Neuropathological Change
EFFA	Efficacy Analysis Population for Accuracy Evaluation
EFFP	Efficacy Analysis Population for Precision Evaluation
SAC	Supplementary Academic Cohort
PET	Positron Emission Tomography
PPV	Positive Predictive Value
NPV	Negative Predictive Value
LR+	Likelihood Ratio Positive
LR-	Likelihood Ratio Negative
FN	False Negative
TN	True Negative
FP	False Positive
TP	True Positive

2. INTRODUCTION

In prior clinical studies supporting accuracy and reliability of flortaucipir F 18 positron emission tomography (PET) scans, interpretation has been shown to have acceptable performance when compared to the autopsy truth standard (TS).

This study is designed to further evaluate the accuracy and reliability of multiple readers' interpretations of flortaucipir F 18 PET scans not only from those subjects who came to autopsy, but also in the intended population for clinical use.

The purpose of this statistical analysis plan (SAP) is to describe the statistical analyses for this study. The SAP should be read in conjunction with the protocol.

3. STUDY OBJECTIVES

3.1. Primary Objective

There are two co-primary objectives for this study:

- Test the relationship between ante-mortem flortaucipir F 18 PET imaging and tau neurofibrillary pathology associated with Alzheimer's disease (AD), as measured at autopsy.
- Assess inter-reader reliability

3.2. Secondary Objective

There are four secondary objectives for this study:

- Test the relationship between ante-mortem flortaucipir F 18 PET imaging of an AD pattern with uptake beyond the temporal/occipital regions (i.e., τAD^{++} ; refer to Protocol Table 1) and tau neurofibrillary pathology associated with Alzheimer's disease (AD), as measured at autopsy
- Assess inter-reader reliability for scans with an AD pattern that is beyond the temporal/occipital regions (i.e., τAD^{++} ; refer to Protocol Table 1)
- Assess agreement among readers of flortaucipir F 18 PET scans in subjects known to be from the intended population (interpretation of scans from Avid study ^{18}F -AV-1451-A05 [Study A05])
- Assess intra-reader reliability for scans read twice by each reader

4. STUDY DESIGN

All training and reads will be conducted by an imaging contract research organization (CRO) as described in the imaging review charter (IRC). Five readers will be trained in-person on the flortaucipir F 18 PET scan read methodology using the previously developed read method. The training will consist of teaching the readers the steps of interpretation, followed by a practice session using a set of demonstration and practice cases. After the training phase is complete, readers will then independently read 262 scans; 83 from Study ^{18}F -AV-1451-A16 (A16) and 159 from Study A05.

The study population for the A16 Study (^{18}F -AV-1451-A16: “A Clinico-Pathological Study of the Correspondence Between ^{18}F -AV-1451 PET Imaging and Post-Mortem Assessment of Tau Pathology”) consisted of subjects at the end of life, who were imaged with flortaucipir F 18 and came to autopsy. Subjects were enrolled in the study with the intent of capturing a range of tau neurofibrillary pathology in AD.

The study population for the A05 Study Confirmatory Cohort (^{18}F -AV-1451-A05 “An open label, multicenter study, evaluating the safety and imaging characteristics of ^{18}F -AV-1451 in cognitively healthy volunteers, subjects with Mild Cognitive Impairment, and subjects with Alzheimer’s disease”) consisted of subjects with cognitive impairment who had Mild Cognitive Impairment (MCI) or dementia with a suspected neurodegenerative cause, and a Mini Mental State Examination (MMSE) score of 20-27, inclusive. Subjects were imaged with flortaucipir F 18 and followed longitudinally for 18 months to assess the subsequent rate of cognitive decline.

5. SAMPLE SIZE JUSTIFICATION

Assuming 80% sensitivity and 80% specificity, 14 truth standard (TS) positive or TS negative cases will be needed to show the lower bounds of 95% confidence interval (CI; 2-sided) greater than 50%, for either sensitivity or specificity, with a Wilson score method to calculate the 95% CI. Out of the 83 A16 cases with autopsy results, 47 were neurofibrillary tangle (NFT) stage B3 per pathologist's panel diagnosis (TS positive for primary objective #1 efficacy analysis #1), and 36 were NFT stage B2 or lower (TS negative for primary objective #1 efficacy analysis #1); 41 were high AD neuropathologic change (ADNC) according to panel diagnosis (TS positive for primary objective #1 efficacy analysis #2), and 42 were low to intermediate ADNC (TS negative for primary objective #1 efficacy analysis #2). Therefore, this sample size provides adequate power to assess the accuracy of flortaucipir F 18 PET scan in detecting underlying pathological changes.

Fleiss' Kappa will be used to assess the inter-reader reliability in flortaucipir F 18 scan visual interpretation. Five independent qualified physicians will read 242 unique scans (83 autopsy scans from study A16 and 159 scans from study A05). Assuming the Fleiss' kappa is expected to be 0.7, this sample size provides over 90% power in detecting a kappa value greater than or equal to 0.60, under a two-sided type I error rate of 0.05.

6. FLORTAUCIPIR PET SCAN SELECTION

Flortaucipir F 18 PET scans were selected from subjects enrolled in previous studies ^{18}F -AV-1451-A16 and ^{18}F -AV-1451-A05. The following images will be used for this study:

- All 83 subjects from Study A16 (primary and supplemental) who have a valid scan and autopsy. This includes:
 - 3 front-runners
 - 64 main study autopsy cases
 - 16 autopsy cases collected under SAC
- All 159 subjects from the study ^{18}F -AV-1451-A05 who have a valid scan, representing the intended population for clinical use.
- 20 scans will be randomly selected (by simple random selection method) from studies A16 and A05, to be read twice independently by each of the 5 readers for intra-reader reading reliability evaluation purposes.

The majority read results from A05 and A16 both showed a ~56% scan positive ($\tau\text{AD}^+/\tau\text{AD}^{++}$) rate. Similarly, it is expected that the 20 scans randomly selected for intra-reader reliability evaluation will have a similar scan positive rate. If by chance the randomly selected 20 cases have a skewed positive or negative rate, to avoid possible interpretation bias from a sample population of primarily positive or negative scans, the random sampling process will be repeated to ensure a relatively balanced positive/negative rate from the selected samples (scan positive rate by majority reads from corresponding study is in the range of 30% - 70%).

An external CRO will randomize all scans into a randomized sequence for visual reading.

7. DEFINITIONS AND CONVENTIONS

7.1. General Summary Table and Individual Patient Data Listing Considerations

Summary tables and listings will be prepared according to ICH Guideline E3 that will include a footer providing the following notes:

1. Date of output generation.
2. SAS program name that generates the output.
3. Reference to the data listings that the summary table based on.
4. Any other output specific details that require further elaboration.

